6.7.6 BBSS Physician Reported Scores

Physician reported BBSS component scores (pelvic tenderness and induration) and total score and the change from baseline in each will be summarized.

The statistical significance of the change from baseline within treatment groups will be based on a paired t-test or Wilcoxon signed-rank test, as appropriate. The change from baseline will be compared between groups using a t-test or Wilcoxon rank-sum test, as appropriate.

6.7.7 VAS

VAS pain assessment scores and the percentage change from baseline will be summarized.

The statistical significance of the percentage change from baseline within treatment groups will be based on a paired t-test or Wilcoxon signed-rank test, as appropriate. The percentage change from baseline will be compared between groups using a t-test or Wilcoxon rank-sum test, as appropriate.

6.8 SAFETY ANALYSES

The safety analyses will be conducted using the Safety population, as defined in Section 4.2.

6.8.1 Adverse Events (AEs)

Treatment-emergent AEs (TEAEs) are defined as those AEs with an onset date and time equal to or after the start of study medication in stage 2, or those events in which the onset date and time are before the start of study medication but worsened after the start of study medication. To be conservative, in the case of a missing onset time for an AE, an AE with a start date equal to or after the dosing date will be considered treatment-emergent. AE's with missing onset dates will also be considered treatment-emergent.

All TEAEs will be summarized by treatment group. The number of TEAEs as well as the number and percentage of subjects who experienced at least one TEAE will be summarized for each system organ class and each preferred term. The percentage will be based on the number of subjects included in the Safety population. Each subject will contribute at most one count per summarization category.

If a subject has more than one AE that codes to the same preferred term, the subject will be counted only once for that preferred term. Similarly, if a subject has more than one AE within a system organ class category, the subject will be counted only once for that system organ class category.

TEAEs will also be summarized by maximum severity and by strongest relationship to treatment. Serious adverse events (SAEs) will be tabulated and listed in a manner similar to TEAEs. A listing of all AE data will be provided to supplement the tabulated results.

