1. INTRODUCTION

This statistical analysis plan (SAP) describes the data analysis specifications for stage 2 of study ZPE-202, entitled “A Phase 2, Multi-Center, Three-Arm, Parallel Design, Randomized, Double-Blind Study to Evaluate the Safety and Efficacy of 6 and 12 mg Proellex® (Telapristone Acetate) Administered Orally in the Treatment of Premenopausal Women with Confirmed Endometriosis”. The preparation of this version of the SAP adheres to Amendment 9 of the ZPE-202 protocol.

Two separate analyses are planned. The first analysis will occur once all subjects have completed the placebo-controlled (stage 2) portion of the study, and will only include data from the placebo-controlled (stage 2) and baseline assessment (stage 1) portions of the study. The second analysis will occur once all subjects have completed the active treatment portion of the study (stage 3), and will include all data collected during the study.

This SAP will focus on analyses for stage 2. Another SAP will focus on analyses for stage 3.

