3. STUDY DESIGN

3.1 OVERVIEW AND LENGTH OF STUDY

ZPE-202 is a phase 2, 3-arm study with an 18 week active dosing period and an option to extend treatment for 2 additional cycles. The study will be conducted in three stages.

In the first stage, women will undergo a baseline assessment period with placebo or no study medication until their second ovulation event. Endometriosis pain, dysmenorrhea, non-

[REDACTED]

In the second stage (placebo-controlled), following the baseline assessment period, subjects will be randomized into one of 3 arms (placebo, 6 mg Proellex, 12 mg Proellex) in a 1-1-1 fashion. The start of the 18 week dosing period for the first cycle of treatment should commence as soon after ovulation as possible, after which subjects will be followed until menses returns. Subjects who do not wish to receive additional cycles of treatment after stage 2 will have their last visit scheduled after blood flow has stopped. During this off-drug interval subjects will continue to record study information in the daily diaries.

After completing a minimum of 28 days of treatment in the second stage of the study, subjects may discontinue the study and still be eligible to qualify for 2 additional treatment cycles.

In the third stage (active treatment), subjects who are eligible to receive additional cycles of treatment and who elect to continue treatment will be scheduled to start dosing in their next course 21 days (+/- 2 days) after the start of bleeding, following the first menses after the end of

their first course of treatment (off-drug interval). Subjects will receive 2 courses of additional active treatment separated by an off-drug interval (ODI), after which they will continue to record study information in the daily diary. Subjects randomized to placebo in the second stage will receive 12 mg of Proellex in this stage. Those randomized to Proellex in the second stage will retain their current dose level for the duration of this stage. The final follow-up visit will be scheduled after blood flow has stopped.

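### SAP 6.8.1 counts every adverse event with a missing onset date as a Stage 2 TEAE, even one whose stop date shows that it ended before the first Stage 2 dose

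*SAP*

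**What the plan says.** SAP 6.8.1 defines treatment-emergent events first as "those AEs with an onset date and time equal to or after the start of study medication in stage 2". It adds events that began earlier but worsened after study medication started. It then gives two rules for incomplete onset data, introduced as conservative:

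- Time missing, date present: "an AE with a start date equal to or after the dosing date will be considered treatment-emergent".
- Date missing: "AE's with missing onset dates will also be considered treatment-emergent".

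TEAEs are reported by treatment group, as counts of events and as number and percentage of women in the Safety population. A listing of all AE data accompanies the tables.

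On scope, SAP Section 1 says that the first analysis "will only include data from the placebo-controlled (stage 2) and baseline assessment (stage 1) portions of the study", and continues: "This SAP will focus on analyses for stage 2. Another SAP will focus on analyses for stage 3". SAP 3.1 describes Stage 1 as follows: "women will undergo a baseline assessment period with placebo or no study medication until their second ovulation event".

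**The concern.** The missing-time rule still checks the date against dosing. The missing-date rule checks nothing, although the record may hold a stop date, a partial onset date or the visit at which the event was first noted. An event that demonstrably finished in Stage 1 is then charged to the arm to which the woman was later randomized.

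The rule is conservative in one sense only: it avoids missing on-treatment events. For a comparison with placebo, adding pre-dose events to all arms makes the arms look more alike, which is not the cautious direction for detecting a drug effect on safety. What is at stake is the descriptive comparison of TEAE incidence between arms.

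A related gap is that the definition gives the TEAE window a start but no end.

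**Working it through.** The plan gives no figure for this point, so there is none to reproduce. The check is mainly of the text, with a small calculation for scale.

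**1. Can pre-dose events be in the data?** Yes.
- SAP Section 1 includes Stage 1 data in the first analysis.
- The latest protocol version, Section 11.1.3, has SAEs documented from informed consent.
- SAP 6.8.1 itself provides for events with onset before study medication.
- Protocol 11.1.1 asks for the duration of each AE, so information bearing on the stop date should often exist.

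**2. What does the rule do with them?** Write D2 for the first Stage 2 dose.

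| Onset information | Other information | Result under SAP 6.8.1 |
|---|---|---|
| Full date before D2, no worsening | – | Not a TEAE |
| Date present, time missing | – | Date compared with dosing date |
| Date missing | Stop date before D2 | TEAE |
| Date missing | None | TEAE |

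The third row is the error. Onset cannot be later than stop, so stop before D2 implies onset before D2. An event that had ended by D2 cannot have worsened after it. The event fails both limbs of the definition and is still counted. The fourth row is a reasonable default.

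**3. What can other dates show?** A stop date, or the visit of first recording, bounds onset only from above.
- If that bound lies before D2, onset was before D2. An event first recorded before D2 may still have worsened later, so the worsening rule must continue to apply.
- If that bound lies in Stage 3, onset could still have been in Stage 2. Excluding on that basis could lose a true Stage 2 event. Only a partial onset date can place onset after the first Stage 3 dose.

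**4. Scale for one woman.** With the planned 20 per arm (SAP 3.2), a woman with no other TEAE who is wrongly counted moves her arm by 1/20 = 5 percentage points. Two such women move it by 2/20 = 10 points, and three by 3/20 = 15 points.

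**5. Scale if the error is equal across arms.** Let p be the true incidence and m the share of otherwise event-free women who gain a false TEAE. Observed incidence is p + (1 − p)m, so the difference between two arms shrinks by the factor (1 − m). The values below are assumptions, not document figures: 30% on placebo and 50% on drug.

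| m | Placebo | Drug | Difference |
|---|---|---|---|
| 0 | 30.0% | 50.0% | 20.0 points |
| 5% | 33.5% | 52.5% | 19.0 points |
| 10% | 37.0% | 55.0% | 18.0 points |
| 20% | 44.0% | 60.0% | 16.0 points |

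The narrowing is slight unless m is large, and nothing in the documents suggests that it is.

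**The case against.** **The effect is limited.** Protocol 11.1.1 requires onset on a 24-hour clock for every AE, so a wholly missing date should be uncommon. The same section ties AE recording to use of the investigational drug, and only SAEs are explicitly collected from consent, so non-serious Stage 1 events may be sparse. Randomization should balance pre-dose errors on average. SAP 6.8.1 plans counts and percentages with no between-arm test, and the full listing keeps a misplaced event visible. All of this stands and argues for a small effect. It does not make the classification correct, and a listing does not correct a table. Balance on average is also little comfort when one woman is worth 5 points.

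**Date conventions may sit elsewhere.** The available SAP text skips from 6.7 to 6.7.3 and ends at 6.8.1, so a general rule on dates could be in text not shown. That cannot be excluded. As it reads, the sentence in 6.8.1 is unconditional and points to no other rule. The visible text is silent on partial dates; it does not say that they count as missing.

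**Stronger readings that a reader might infer.**
- *Stage 3 events on 12 mg end up in the placebo column.* The ingredients seem to be there: "Subjects randomized to placebo in the second stage will receive 12 mg of Proellex in this stage", women may move on after as little as 28 days of Stage 2 treatment, and the first analysis waits for all women to finish Stage 2. But SAP Section 1 confines this analysis to Stages 1 and 2, so an event that other information places in Stage 3 is outside these tables. What remains is narrower: 6.8.1 gives no end of window to put that restriction into practice, and the SAP does not say how an undated event is assigned to a stage when nothing else settles it.
- *Stage 1 is untreated.* SAP 3.1 allows placebo or no study medication. Either way, the events precede randomized treatment.
- *A sizeable share of TEAEs is affected.* If Stage 1 is assumed to last 4 to 8 weeks and undated events are spread evenly over it and the 18 dosing weeks, 4/22 = 18% to 8/26 = 31% of them are pre-dose. Adding about 3 weeks of follow-up until menses returns gives 4/25 = 16% to 8/29 = 28%. These are shares of an unknown number of undated events, under an even spread that is doubtful. They do not estimate the effect on any arm.

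**Conclusion.** The point holds for pre-dose events, as a minor one. The stated rule misclassifies any undated event whose stop date precedes the first Stage 2 dose, and it does so although the record shows the right answer. The consequence is a slight dilution of the between-arm AE comparison, plus chance imbalance in small arms. The total size is unknown because the number of undated events is not given; it is probably small. The 5-point figure rests on the planned 20 per arm and on the woman having no other TEAE in the category.

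On the Stage 3 side, the documents support only a request to state the end of the window. They do not support a claim that events known to fall in Stage 3 will be charged to placebo.

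**What to change.** Replace the missing-date sentence in SAP 6.8.1 with:

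> An AE with a missing or partial onset date is treatment-emergent unless its partial onset date, its stop date or the visit at which it was first recorded shows that it began before the first Stage 2 dose, subject to the existing worsening rule.

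Add an end to the Stage 2 TEAE window that matches the data scope in SAP Section 1: the first Stage 3 dose, or the final Stage 2 visit for women who do not continue. State that an event without a full onset date is excluded as a Stage 3 event only when a partial onset date places its onset after the first Stage 3 dose. A stop date or recording visit in Stage 3 is not enough.

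Events that no information can place stay treatment-emergent, so the conservative default is kept where it is needed. The cost is a few sentences and a small programming change, to be settled before the Stage 2 data are unblinded.

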Subjects who complete at least 28 days after Visit 3 and wish to discontinue treatment due to lack of efficacy will be eligible to start active treatment (stage 3). Subjects who discontinue the study prior to this date will not be eligible for additional treatment.

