4.2 SAFETY POPULATION

The Safety population will consist of all patients who are randomized, receive study drug, and have some post-baseline safety data.

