6.3 EXTENT OF EXPOSURE

The duration of exposure will be calculated for each subject. Summary statistics will be presented using the Intent-to-Treat population.

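### Stage 2 adverse event percentages take no account of time on study, so the arms cannot be read side by side if lack-of-efficacy exits from day 28 differ between them

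*SAP*

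**What the plan says.** SAP 6.8.1 sets the measures, "The number of TEAEs as well as the number and percentage of subjects who experienced at least one TEAE will be summarized", and the denominator: "The percentage will be based on the number of subjects included in the Safety population". Serious events are tabulated in a similar way. The TEAE definition gives a start (first Stage 2 medication) but no end to the window.

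SAP 4.2 sets no minimum exposure for that denominator: "The Safety population will consist of all patients who are randomized, receive study drug, and have some post-baseline safety data".

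On time under observation, SAP 3.1 describes the planned course, "ZPE-202 is a phase 2, 3-arm study with an 18 week active dosing period", and an early way out: "After completing a minimum of 28 days of treatment in the second stage of the study, subjects may discontinue the study". They still qualify for Stage 3. Protocol 8.2.1 (Amendment 9, which the SAP follows) ties this route to a reason. It covers women past day 28 who "wish to discontinue treatment due to lack of efficacy will be eligible to start active treatment (stage 3"). Women who were on placebo then receive 12 mg.

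SAP section 1 says the first analysis "will only include data from the placebo-controlled (stage 2) and baseline assessment (stage 1) portions of the study". SAP 6.3 says "The duration of exposure will be calculated for each subject". That summary uses the Intent-to-Treat population, does not say that it is by arm, and is not linked to the adverse event tables.

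**The concern.** A woman observed for 4 weeks and a woman observed for 18 weeks each add one to the denominator, but the first has had far less time to report an event. This would matter little if early exit were unrelated to treatment. Here the protocol provides an exit for lack of efficacy that leads to active drug. If the drug works, that exit is likely to be used more on placebo.

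Safety is part of the stated objective, and the by-arm TEAE table is where readers will look for the drug-placebo contrast. If leaving differs by arm, part of any gap in that table reflects follow-up time and not the drug. The TEAE count shown beside the percentage depends on follow-up in the same way.

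**Working it through.** The plan states no event rate, exit rate or event timing, so there is no figure of its own to reproduce.

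**Inputs from the documents.** Planned Stage 2 dosing is 18 weeks = 126 days (SAP 3.1). The earliest exit that keeps Stage 3 eligibility is day 28 (SAP 3.1, protocol 8.2.1). There are 20 women per arm (SAP 3.2). A woman who leaves at day 28 has 28/126 = 22.2% of planned exposure.

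**Assumptions.** The arms have the same true hazard, constant over time. *p* is the 18-week risk. *f* is the share of an arm that leaves early. Exit is unrelated to having an event.

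**Formulae.** λ = −ln(1−p)/18 per week. The risk *r* observed in a leaver is:
- all leave at week 4: r = 1 − exp(−4λ)
- exits spread evenly over weeks 4 to 18: r = 1 − [exp(−4λ) − exp(−18λ)]/(14λ)

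Crude arm percentage = (1−f)p + f·r. The false difference between arms is therefore (f₁ − f₂)(p − r).

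**Main case, p = 50%, 30% against 10% leaving.** λ = 0.6931/18 = 0.03851.
- Week-4 exits: r = 1 − 0.857 = 0.143. Crude: 0.7×0.5 + 0.3×0.143 = 39.3% against 0.9×0.5 + 0.1×0.143 = 46.4%. The difference is 7.1 points, or 1.4 women of 20.
- Spread exits: r = 1 − (0.857 − 0.500)/0.539 = 0.337. Crude: 45.1% against 48.4%. The difference is 3.3 points, or about 0.7 women of 20.

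**Range of false differences, in points.**

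| 18-week risk | Leaving | All at week 4 | Spread over weeks 4-18 |
|---|---|---|---|
| 50% | 20% vs 5% | 5.4 | 2.4 |
| 50% | 30% vs 10% | 7.1 | 3.3 |
| 50% | 40% vs 10% | 10.7 | 4.9 |
| 10% | 20% vs 5% | 1.2 | 0.6 |
| 10% | 30% vs 10% | 1.5 | 0.8 |
| 10% | 40% vs 10% | 2.3 | 1.1 |

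**Off-drug follow-up.** If every woman is also observed for 21 days off drug, a day-28 leaver has 49 days and a completer 147. Taking 50% as the risk over 147 days, r = 1 − 0.5^(49/147) = 0.206. The 30% against 10% difference is then 0.2 × (0.5 − 0.206) = 5.9 points with all exits at day 28.

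**When the effect vanishes.** If all events occur in the first 28 days, r = p and the difference is zero. A woman who leaves because of an event is already counted in the numerator.

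**What person-time does.** Take p = 40% and 40% against 10% leaving at day 28. The crude percentages are 28.3% and 37.1%. A simulation of first events per patient-week at risk gave 2.84 per 100 patient-weeks in both arms, and the true value is −ln(0.6)/18 = 2.84 per 100.

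**Where a rate would mislead.** Suppose the hazard is not constant: half of each arm has its event near week 1 and none occur later. Mean follow-up with week-4 exits is 0.7×18 + 0.3×4 = 13.8 weeks against 0.9×18 + 0.1×4 = 16.6 weeks. Time at risk per woman is 0.5×1 + 0.5×13.8 = 7.4 weeks against 0.5×1 + 0.5×16.6 = 8.8 weeks. Equal-risk arms then show rates in the ratio 8.8/7.4 = 1.19, so a rate alone is not enough.

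**The case against.** The crude table is the ordinary adverse event table, and no test of events between arms is planned. The SAP already calculates exposure (6.3), summarizes early discontinuation (6.4), lists all adverse event data (6.8.1) and allows further analyses (6.1). With 20 women per arm, unequal follow-up would not stay hidden for long. The second analysis will include all data, so events after transfer are not lost. Leaving them out of the Stage 2 placebo column is right, because they occur on active drug.

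The size is also modest. In the main case the standard error of the difference is √(0.393×0.607/20 + 0.464×0.536/20) ≈ 16 points, against a bias of 3 to 7. Single preferred terms will usually carry lower risks than 50%.

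Much of this stands. It limits the point to a descriptive contrast and makes the remedy an addition, not a correction. It does not remove the point. The exposure summary is in a different population, is not said to be by arm, and is not set beside the event tables. A listing does not give a comparison on equal time. The bias is also systematic, unlike sampling error, and affects every term with onset after day 28.

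A reader might infer more than the documents support:
- *The contrast is biased.* Differential exit is possible under the design but is not shown.
- *The table hides harm from the drug.* If placebo loses more women, the error runs against the drug.
- *Any dose with many early withdrawals looks safer.* This fails where women withdraw because of an event, since they are already counted.

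The SAP text available ends at 6.8.1, so any later safety section could not be checked.

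**Conclusion.** The point holds in a limited form. SAP 6.8.1 uses a head-count denominator in a design that lets women leave for lack of efficacy after 22% of planned dosing. If those exits differ by arm, the percentages are not comparable, and the arm with more leavers shows too few events.

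Under equal constant hazards, the assumed risks of 10% and 50%, and the assumed exit shares, the false difference runs from 0.6 to 10.7 points. The main case gives about 3 to 7 points, roughly one woman of 20. Counting off-drug follow-up or assuming early-onset events makes it smaller. Exit shares, risks and timing are all assumptions. No planned test or decision rule fails, so this is a cheap improvement to safety reporting.

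**What to change.** Keep the crude TEAE table and add to SAP 6.8.1:

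- **(a)** The same table restricted to days 1-28 of Stage 2, before the transfer route opens. It needs no hazard assumption. It says nothing about later events, so it cannot stand alone.
- **(b)** For any TEAE, SAEs and common terms, women with a first event per 100 patient-weeks by arm. Time at risk runs from first Stage 2 dose to the first event or last Stage 2 dose, whichever is earlier. A Kaplan-Meier summary of time to first event would serve instead and avoids the constant-hazard assumption. Show events in the off-drug interval before any Stage 3 dose separately. Pooling off-drug time would dilute the rates most in the arm with more leavers: with an assumed 6-week interval it is 6/10 = 60% of a day-28 leaver's time but 6/24 = 25% of a completer's. This also gives the event window the end that 6.8.1 does not state.
- **(c)** Duration of exposure by arm in the Safety population, placed beside the adverse event table.

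The cost is a few extra descriptive tables from data already collected. The rates will be imprecise at 20 women per arm, and (b) as a rate assumes a roughly constant hazard. No clinical rule changes.
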